Protocol version 1.0 dated 29/10/2018

Sponsor: University Hospitals of Leicester

Background

Even a simple local anaesthetic procedure is associated with much anxiety for the patient involved. This is compounded by the process of local anaesthetic injection which involves not only the pain of the needle puncture but the stinging sensation as the local anaesthetic is infiltrated into the site. Many methods of easing this pain have been used such as using smaller gauge needles, slow infiltration, buffering the anaesthetic and prior application of local anaesthetic creams.

There has been a lot of research conducted in dentistry which has shown the effectiveness of Transcutaneous Electronic Nerve Stimulation (TENS) as an anaesthetic agent. But the research has not extended to other fields of surgery such as in minor local anaesthetic cases.

Aim

TENS-LA trial will be able to provide evidence regarding the possible efficacy of TENS as a local anaesthetic and its ability to alleviate the pain associated with local anaesthetic injection. The effectiveness will also be compared to that of local anaesthetic cream which is being used at present prior to local anaesthetic injections.

Outcome

Primary Outcome: The primary outcome is pain of local anaesthetic injection after application of TENS or LA cream as measured by two Numeric Pain Rating Scale Secondary Outcomes: Changes in blood pressure and pulse rate in response to injection of local anaesthetic

Trial Design

A prospective randomised controlled trial.

Diagnosis and Inclusion/Exclusion Criteria

Adults 18-90 years of age undergoing a split skin graft harvest from the thigh under local anaesthesia will be included

- who do not have a pacemaker or ICD
- who are not pregnant
- with no history of epilepsy, aneurysm
- with no history of allergy to local anaesthetic or TENS electrodes

Test device and Mode of usage

A hand-held battery-powered CE-approved TENS device will be used. Eligible patients who have been randomised to the test arm of the study will have the electrodes attached to the area adjacent to the skin graft donor site 30 minutes before injection of local anaesthetic.

Setting

The trial will be conducted in Leicester Royal Infirmary, UK

Duration of treatment

The TENS treatment is over a minimum period of 30 minutes from attachment of electrodes to administration of local anaesthetic.

The LA cream treatment is over a minimum period of 60 minutes from application of the cream to administration of local anaesthetic.

Evaluation Criteria

The effectiveness of the treatment is assessed using two Numeric Pain Rating Scale in the study and control groups. Pulse rate and Blood Pressure monitoring will be carried out as an objective measurement of the response to pain.

Planned trial start date

1st May 2019

Planned date of last outcome

30th April 2020

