2.3 SAMPLE SIZE

The study is designed to detect a difference of 3 units in pain scale between the 2 groups at 0.05 significance level and 90% power. We assume the standard deviation as 3 and the number of participants in each group has been calculated as 22. The total number of the patients including both arms of the trial will be 44.

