2.8 TRIAL INTERVENTION

On the day of procedure, either the Chief Investigator or Investigator will see the patient in the Theatre Arrivals area and have a full discussion on the details of the trial and will answer all their questions. Patients willing to take part and are within the inclusion criteria and does not have any of the exclusion criteria will be randomised to either the study group or the control group after obtaining informed consent.

The trial group will have the TENS to the area planned for injection for at least 30 minutes before injection of the local anaesthetic.

The control group will have EMLA 5% applied on the site planned for local anaesthetic injection and after a minimum period of 1 hour, will be removed and immediately injected with the same anaesthetic solution (this is already a procedure practiced by some of the surgeons).

Pain perception will be evaluated using two Numeric Pain Rating Scales in the study and control groups- one to assess the pain of needle penetration and the second to assess the pain of local infiltration. The Numeric pain scale is filled in by the doctor as indicated by the patient. Pulse rate and Blood Pressure monitoring will be carried out as an objective measurement of response to pain (these are routinely recorded when patient is in the theatre for a procedure). Patient involvement in the study ends at this point.

Analysis of the outcome will be done at the end of the trial period.

Description of device

The TENS unit comprises of an

- (1) Electric pulse generator which is battery-operated and programmable for pulse rate, width and intensity.
- (2) Lead wires connecting the unit to electrodes
- (3) Electrodes which consists of silicone rubber and adhesive to attach to skin surface.

Specifications of the unit to be used.

The device to be used in the trial is Neurotrac TENS Unit

Power supply : PP3 Alkaline battery, 9 volts

Pulse rate : 80Hz -100Hz

Pulse width : 50 - 300 microsecondsAmplitude : 0-80mA (500 Ohm load)

Type : Continous

Contraindications

1. In patients with pacemakers or implantable cardioverter-defibrillators (ICDs)¹⁴. This is of utmost significance for use in thoracic area as there will be interference with the electrical impulses generated except in fixed rate pacemakers.

- 2. Epileptic patients as there is a risk of triggering a seizure.
- 3. Patients with history of aneurysm. TENS stimulates peripheral blood flow and hence can be problematic in such cases.

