2.10 OUTCOME ASSESSMENT

Pain perception will be evaluated using two Numeric Pain Rating Scales in the study and control groups. One scale will assess the pain caused by needle piercing the skin and the second will do so for the pain caused by infiltration of local anaesthetic agent.

Pulse rate and Blood Pressure monitoring will be carried out as an objective measurement of response to pain.

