2.13 ANALYSIS

The analysis will assess the effectiveness of TENS in alleviating the pain of local anaesthetic injection with the differentiation of needle and infiltration pain and also compare the TENS with EMLA. It is expected that TENS will alleviate or bring about a significant reduction in the pain associated with injection of local anaesthetic and will be better or as effective as EMLA in this aspect. This is the hypothesis being examined in this trial.

Pain perception will be evaluated using two Numeric Pain Rating Scales in the study and control groups. Pulse rate and Blood Pressure monitoring will be carried out as an objective measurement of response to pain.

The tabulation of the results will be done by the research team after transcribing to an excel spreadsheet and the fully anonymised data will be analysed statistically by the biostatistician at The University of Leicester.

Summary statistics of 2 groups will be presented. Median score, lower and upper quartile and minimum and maximum scores will be given for each group. Two groups will be compared using Mann Whitney test.

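### The primary outcome is two unranked pain scales, but the sample size serves one unnamed scale and no rule says which scale, or whether one or both, decides the result

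*Protocol*

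**What the plan says.** The Outcome paragraph of the protocol's opening summary gives this definition: "The primary outcome is pain of local anaesthetic injection after application of TENS or LA cream as measured by two Numeric Pain Rating Scale". The Evaluation Criteria paragraph repeats the pair without an order: "The effectiveness of the treatment is assessed using two Numeric Pain Rating Scale in the study and control groups".

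Section 2.8 defines the two scales: "one to assess the pain of needle penetration and the second to assess the pain of local infiltration". Section 2.10 says the same: "One scale will assess the pain caused by needle piercing the skin and the second will do so for the pain caused by infiltration".

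Section 2.3 sets the sample size to "detect a difference of 3 units in pain scale between the 2 groups at 0.05 significance level and 90% power", with one assumed standard deviation of 3, giving 22 per group and 44 in total. The scale is singular and is not named.

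Section 2.13 keeps the two pains apart, promising to assess TENS in "alleviating the pain of local anaesthetic injection with the differentiation of needle and infiltration pain". The only test statement is: "Two groups will be compared using Mann Whitney test".

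**The concern.** The outcome definition has two scales and the sample-size statement has one. Nothing in the protocol ranks the scales, combines them, divides the significance level, or says whether success needs one or both.

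If needle pain differs significantly and infiltration pain does not, or the reverse, the protocol cannot say whether the primary outcome was met. The choice could then be made after the data are seen. The background itself treats puncture and infiltration as distinct sources of pain, so a split result is plausible. The Rationale also ties future use of TENS to a statistically significant benefit over EMLA, so the trial's main conclusion depends on this choice.

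**Working it through.** **Inputs from the protocol.** Difference 3, SD 3 (standardised effect 1), significance level 0.05, power 90%, 22 per group (2.3); Mann-Whitney test (2.13).

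**Assumptions.** The test is two-sided (this reproduces 22; one-sided gives 18). Each scale is tested at 0.05, the only level given. Scores are normal in the simulations (40,000 runs). The correlation r between the scales is not in the documents and is varied. Both scores come from one patient and one injection, which favours a higher r.

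**1. The plan's own figure.** n = 2 × (1.96 + 1.2816)² × (3/3)² ≈ 21.0, rounded up to 22. This matches. At 22 per group the exact t-test power is 0.8997 and the simulated Mann-Whitney power is 0.883. The calculation therefore covers one comparison at the full 0.05.

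**2. Either scale suffices.** Type I error is 1 − P(|Z₁| ≤ 1.96 and |Z₂| ≤ 1.96). At r = 0 this is 1 − 0.95² = 0.0975.

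**3. Both scales are needed.** At r = 0 power is the product: 0.8997² = 0.81 (t-test) and 0.883² = 0.78 (Mann-Whitney). Other values of r are simulated.

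**4. Split results.** With a 3-unit effect on both scales, P(exactly one significant) = 2 × (single-scale power − both-scale power). At r = 0 this is 2 × (0.883 − 0.779) = 0.208, and 0.207 by simulation.

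| r | Either suffices: type I error | Both needed: t-test power | Both needed: Mann-Whitney power | Exactly one significant (Mann-Whitney) |
|---|---|---|---|---|
| 0 | 9.75% | 81% | 78% | 21% |
| 0.5 | 9.1% | 83% | 80% | 16% |
| 0.8 | 7.8% | 86% | 83% | 10% |
| 0.9 | 7.0% | 87% | 84.5% | 8% |

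If only one scale has an effect, a split is the usual result. At r = 0 its probability is 0.883 × 0.95 + 0.117 × 0.05 = 0.845; by simulation it is 0.858 at r = 0.5 and 0.870 at r = 0.8.

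**5. Rules that could keep both 5% and about 90%.**
- One named scale: 22 per group stands as calculated.
- Mean of the two scores: the standardised effect becomes √(2/(1 + r)). Mann-Whitney power is 99%, 95%, 91% and 90% at r = 0, 0.5, 0.8 and 0.9 with an effect on both scales, but only about 60%, 44% and 38% at r = 0, 0.5 and 0.8 if one scale alone has it.
- Either scale at 0.025: Mann-Whitney power for at least one is 96%, 92%, 91% and 88% at r = 0, 0.5, 0.6 and 0.8 with an effect on both.

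The protocol fixes none of these.

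**The case against.** The strongest reply is that error splitting, test order and an either-or-both rule are commonly left to a statistical analysis plan, which is not shown. Section 2.3 can also be read kindly: the same difference and SD may be meant for each scale, so that 22 per group gives the stated power scale by scale. The protocol never claims 5% error or 90% power over the pair. The two-scale figures all need an assumed correlation, and at r = 0.8 to 0.9 they are modest: error of 7.0% to 7.8%, and both-needed power of 83% to 84.5% against 88%.

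Much of this is fair. The testing procedure could sit in an analysis plan, the arithmetic for one scale is right, and the error and power figures are illustrations across a range. What does not go away is that the protocol itself sets the primary outcome and the quantity its sample size serves, and the two do not match. A later testing rule would still leave 2.3 without a named scale, and the kind reading still leaves success undefined when the scales disagree.

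Naming a scale also does not settle the separate question of the hypothesis that TENS is better than or as effective as EMLA. A two-sided test on the named scale answers only whether the arms differ.

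**Conclusion.** The concern holds and should be fixed. The 22 per group is correct for one scale at two-sided 0.05, but it is tied to neither of the two scales that make up the primary outcome, and no success rule is given. Without one, the plan does not secure both 0.05 and 90% for the outcome it defines: with each scale tested at 0.05, either the error rises above 5% or the power falls below its single-scale value. The exact size depends on the assumed correlation, normal scores and, for power, a 3-unit effect on both scales. The direction is the same at every correlation examined. The ambiguity cannot be repaired credibly once results by arm are known, which is why a wording gap carries this weight.

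**What to change.** Before recruitment, name one scale as the single primary outcome in the Outcome paragraph and in 2.3, for example:

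> The 22 per group powers the comparison of [needle penetration / infiltration] pain.

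In 2.13, add:

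> The primary scale is tested first at two-sided 0.05; the other scale is tested at 0.05 only if the first is significant.

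This holds the error over both scales at 5% and keeps 44 patients. **Cost:** wording only, except that the second scale cannot be claimed if the first fails. Its power is about 78% to 83% (Mann-Whitney, r = 0 to 0.8) with a 3-unit effect on both. Single-scale power under the planned Mann-Whitney test is about 88%.

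If both scales are to stay primary, use Holm's procedure: the smaller p-value against 0.025, then the other against 0.05, claiming only the scale or scales that pass. Restate Mann-Whitney power at 22 per group as about 85% to 87% per scale if both have a 3-unit effect (r = 0.8 to 0), or about 81% if only one does. **Cost:** no extra patients if that power is accepted. Restoring 90% per scale needs about 24 (t-test) or 25 to 26 (Mann-Whitney) per group at r = 0.5 to 0.8 with an effect on both, and 27 or 28 respectively if one scale alone has it.

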1. INTRODUCTION

Background

Even a simple local anaesthetic procedure is associated with much anxiety for the patient involved. This is compounded by the process of local anaesthetic injection which involves not only the pain of the needle puncture but the stinging sensation as the local anaesthetic is infiltrated into the site. Many methods of easing this pain have been used such as using smaller gauge needles, slow infiltration, buffering the anaesthetic and prior application of local anaesthetic creams.

Study objectives and significance

There has been a lot of research conducted in dentistry which has shown the effectiveness of Transcutaneous Electronic Nerve Stimulation (TENS) as an anaesthetic agent. But the research has not extended to other fields of surgery such as in minor local anaesthetic cases.

TENS has been approved by CE as a method of pain alleviation. The TENS-LA trial will be able to provide reliable evidence on the possible effectiveness of TENS in alleviating pain of local anaesthetic injections and also how it compares with local anaesthetic cream for this purpose. If TENS is found to be effective, it can be used as a simple and safe device in minor surgical procedures to take away the most dreaded part of the procedure-the pain of injections.

TENS is a method of electrical stimulation to provide a degree of pain relief by stimulating either the pain gate mechanism and/or the internal opioid system. It is a non-invasive method with hardly any side effects. The most common side effect reported is allergic reaction (2-3%) to the electrodes, gel or the tapes used for fixing the electrodes

The intensity of current used ranges from 0-80mA into 500 Ohm load. The aim is to depolarise the sensory nerves and for this purpose the small strength provided by the machine is sufficient. This is delivered in pulses. To be clinically effective, the pulse ranges from 2-200 pulses per second (pps) or Hertz (Hz). The duration of each pulse (pulse width) may vary from 50 to 300 microseconds (μ s).

There are two primary pain relief mechanisms: the pain gate mechanism and the endogenous opioid system.

The gate control theory was proposed by Melzack and Wall in 1965^2 . By activation of the A β sensory fibres (large fibres) with non-noxious stimuli the inhibitory interneurons in the dorsal horn are activated and the transmission of the noxious stimulus from the C

fibres (small fibres) inhibited. Thus, selective enhancement of input in large fibres shuts the Pain Gate band diminishes any ongoing pain³.

The alternative mechanism of pain relief by TENS is that it stimulates the release of endogenous opioids in the spinal cord. Low frequency and high frequency TENS function through activation of mu and delta opioid receptors respectively^{4,5}.

TENS was used by Wall and Sweet on patients experiencing pain, increasing the voltage till tingling was experienced in the area and resulted in relief of pain during the stimulation and for 30 minutes after.

The intensity or amplitude of TENS is directly related to the positive effect- a strong intensity (barely comfortable) provides significant analgesic effect.

A systematic review and meta -analysis on the effectiveness of TENS on post-operative analgesia by Bjordal et al⁸ concluded that there is significant reduction in analgesic consumption for post-operative pain when TENS is administered with a strong intensity at an adequate frequency in the area.

TENS was found to be a good alternative to local anaesthetic in children requiring restorative dental procedures in many studies^{9,10}.

TENS was found to be more effective than local anaesthetic gel prior to inferior alveolar block injection in children in reducing the pain of injection in a study by Choudhari et al¹¹ which confirmed the findings from a similar study earlier by Meechan et al¹².

TENS was found to be almost equally effective as 2% local anaesthetic injection during minor paediatric dental procedures and more comfortable and preferred by 93.3% of the patients over the local anaesthetic in a study by Dhindsa et al¹³.

Objectives

The primary aim of this study is to evaluate the possible effectiveness of TENS in reducing the pain associated with local anaesthetic injection and to compare it with the use of topical anaesthetic cream. The hypothesis is that TENS is effective in alleviating/reducing the pain of local anaesthetic injection and more or equally effective compared with local anaesthetic cream for this purpose.

Methods and design

The study is planned as a randomised control trial with 2 arms:

- 1- The control group will have a local anaesthetic cream EMLA (Eutectic Mixture of Local Anaesthetics) applied for a minimum period of 60 minutes before injection of local anaesthetic
- 2- The study group will have TENS applied for a minimum period of 30 minutes before injection of local anaesthetic

Two electrodes will be placed - one proximal and the other distal to the area marked for harvest of skin graft on the thigh a distance of 10 cm.

Conventional treatment mode Programme 1 will be used with a rate of 80Hz -100Hz and pulse width of 200 micro seconds. The intensity will be gradually increased till patient experiences steady continuous stimulation but no muscle contraction. This is maintained for a period of 30 minutes after which the local anaesthetic injection is carried out.

Rationale

Though there have been several publications on the benefits of TENS as a local anaesthetic and also to reduce the pain of local anaesthetic injections, such a research is lacking in the surgical specialties. This trial would help to fill in this gap in evidence and help to make better evidence-based decisions.

If found to have a statistically significant benefit over the use of EMLA to alleviate the pain of local anaesthetic injection, TENS will be the way forward for minor operations for the purpose. The most dreaded part of the procedure for the patient is made more tolerable.

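### The hypothesis claims that TENS works and is at least equal to EMLA, but two active arms and a test of difference can show only superiority over EMLA

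*Protocol*

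**What the plan says.** The Objectives in section 1 give the aim and the hypothesis. The aim begins: "The primary aim of this study is to evaluate the possible effectiveness of TENS in reducing the pain associated with local anaesthetic injection"; comparison with topical cream is added to it. The hypothesis is that "TENS is effective in alleviating/reducing the pain of local anaesthetic injection and more or equally effective compared with local anaesthetic cream".

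Section 2.13 repeats both parts. TENS is expected to alleviate pain or "bring about a significant reduction in the pain associated with injection of local anaesthetic and will be better or as effective as EMLA", followed by: "This is the hypothesis being examined in this trial". The analysis is to assess the effectiveness of TENS "with the differentiation of needle and infiltration pain and also compare the TENS with EMLA". The synopsis (Aim) and section 1 (Study objectives and significance) have the same two-part structure. Section 2.1 is looser but also opens with the efficacy of TENS itself.

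The design is narrower:

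- **Arms** (section 1, Methods and design): "The study is planned as a randomised control trial with 2 arms", EMLA as control and TENS as study group.
- **Sample size** (2.3): set to "detect a difference of 3 units in pain scale between the 2 groups", with SD 3, significance level 0.05 and 90% power, giving 22 per group and 44 in total.
- **Outcome** (2.8, 2.10): two numeric pain scales, one for needle penetration and one for infiltration, both scored at the pre-treated injection.
- **Analysis** (2.13): "Two groups will be compared using Mann Whitney test".

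No equivalence or non-inferiority margin appears, and no figure is given for the effect of EMLA against no pre-treatment. The Rationale in section 1 ties uptake to a significant benefit over EMLA, and section 2.5 describes the trial to patients as a comparison with EMLA.

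**The concern.** The hypothesis contains three claims: TENS reduces injection pain, TENS beats EMLA, or TENS equals EMLA. The first needs a reference without active pre-treatment. The third needs a margin and a confidence interval read against it. The plan has neither, so only the second is tested.

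The problem shows when the arms do not differ. The hypothesis counts that outcome as a possible success, and its wording invites two conclusions the data cannot give: that TENS works and that it is as good as EMLA. The introduction adds to this. Under Study objectives and significance, TENS may be used once found effective, with no mention of a benefit over EMLA; the Rationale asks for that benefit. A null result fails the second condition but could be read as meeting the first.

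**Working it through.** **Inputs.** From section 2.3: difference 3, SD 3, alpha 0.05, power 90%, n = 22 per arm. Assumed here, because the protocol gives no margin: true disadvantages of TENS of 1, 1.5 and 2 points, and margins of 1 to 3 points. The SD is taken to apply to each pain scale.

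**1. The stated sample size.** n = 2 × (z₁₋α/₂ + z₁₋β)² × (SD/difference)².

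- Two-sided: 2 × (1.960 + 1.282)² × (3/3)² = 21.01, rounded up to **22**. This matches the protocol.
- One-sided: 2 × (1.645 + 1.282)² = 17.1, rounded up to 18. This does not match.

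The size is therefore that of a two-sided test of difference.

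**2. Precision.** SE = 3 × √(2/22) = 0.90. The 95% half-width is 2.018 × 0.9045 = **1.83 points** (t, 42 df). An observed difference of exactly zero would still be compatible with TENS being about 1.8 points worse.

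**3. Chance of a non-significant result when TENS is truly worse.** The t-test column uses the noncentral t with noncentrality d/SE. The Mann-Whitney column is simulated with normal scores, 20,000 trials per row, and is accurate to about one percentage point.

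| TENS truly worse by | t-test | Mann-Whitney |
|---|---|---|
| 1 point | 81% | 81% |
| 1.5 points | 63% | 64% |
| 2 points | 42% | 44% |

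Scores rounded and clipped to 0–10, with an assumed EMLA mean of 4, give 82%, 65% and 45%. The normal-score assumption does not drive the result.

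**4. Can 22 per arm support equality?** The middle column is the chance that the 95% confidence interval excludes TENS being worse by margin m when the arms are truly equal (noncentral t with noncentrality m/SE). The last column is the n per arm needed for 90% power, 2 × (1.960 + 1.282)² × 9/m² (normal approximation).

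| Margin m | Chance with 22 per arm | n per arm for 90% |
|---|---|---|
| 1 point | 19% | 190 |
| 2 points | 58% | 48 |
| 3 points | 90% | 22 |

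With truly equal arms, 90% is reached only at a margin as wide as the difference the trial was sized to detect.

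**5. Effect of TENS against no pre-treatment.** Let P be mean pain in each condition. The trial estimates P(TENS) − P(EMLA). The effectiveness claim concerns P(TENS) − P(none). P(none) is not observed in any patient, so no sample size gives a direct estimate.

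**The case against.** The strongest reply is that the working parts of the plan already form a coherent superiority trial. Section 2.3 sizes a difference, section 2.13 tests one, the Rationale requires a benefit over EMLA, and section 2.5 tells patients the comparison is with EMLA. Nowhere does the protocol say a null result will be reported as proof. That is true, and it limits the defect to the aim, the hypothesis and the stated analysis goal. But section 2.13 declares the two-part statement to be the hypothesis examined, so it is more than background prose. The sentence on use of TENS in the introduction is background, and the point does not depend on it.

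Other replies stand in part:

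- **Pulse and blood pressure** are recorded before injection and charted with the pain scores, so they give a within-patient reference for the secondary outcome. They do not supply pain at an injection without pre-treatment.
- **EMLA is an accepted method.** Properly shown non-inferiority to it could support effectiveness indirectly. The protocol plans no such analysis and gives no figure for the effect of EMLA.
- **The 3-point margin result assumes a true difference of zero.** Correct. By the same formula, a true TENS advantage of 1 point would give 90% at a 2-point margin, since 2 + 1 = 3. The result is conditional and is stated so.
- **A statistical analysis plan may settle this.** It could add a margin or an interval. It cannot create an untreated reference, and with truly equal arms, 44 patients leave any margin clearly below 3 points underpowered.

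**Conclusion.** The concern holds. The plan supports the superiority part of its hypothesis and neither of the other two claims. A non-significant result would show neither that TENS reduces injection pain nor that it is as effective as EMLA, and such a result is likely even if TENS is moderately worse: about 81% of trials at 1 point and 44% at 2 points. These figures rest on SD 3 and 22 analysed per arm; the 1- to 2-point disadvantages are illustrations.

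If TENS scores significantly lower, superiority over EMLA is shown. A benefit over no pre-treatment then follows only on the assumption that EMLA does not worsen injection pain. The fault lies in the wording of aim, hypothesis and analysis goal; arms, sample size and test can stay. It should be corrected before results are interpreted.

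**What to change.** Keep the arms, sample size and test, and change the text.

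1. **Aim** (synopsis; section 1, Study objectives and significance, and Objectives; 2.1; 2.13). Restate as: *to compare the pain of local anaesthetic injection after TENS with that after EMLA*.
2. **Hypothesis** (section 1, Objectives; 2.13). Restate as: *pain scores are lower after TENS than after EMLA, tested two-sided*. Remove the claims of effectiveness in itself and of equality with EMLA in both places.
3. **Significance paragraph** (section 1). Tie the statement on use of TENS to a benefit over EMLA, as the Rationale does.
4. **Section 2.13.** Add: *The TENS–EMLA difference will be reported with its 95% confidence interval (Hodges-Lehmann, to match the Mann-Whitney test). A non-significant difference will not be reported as evidence that TENS reduces injection pain, nor that it is as effective as EMLA. If TENS scores lower, any claim of benefit over no pre-treatment will state the assumption that EMLA does not worsen injection pain.*

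The cost is a narrower headline claim (superiority over EMLA, or no conclusion) and, if the protocol is already approved, an amendment under section 2.6. No data collection changes.

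If the sponsor wishes to keep the equality claim, it needs a justified margin, an analysis based on the confidence interval and a matching sample size: for example 48 per arm at an assumed 2-point margin, with no true difference and 90% power. The effectiveness claim would still need a sham or untreated reference, or would have to be dropped.
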